**Group A:**

two vaccinations with MV-ZIKA-RSP, high dose on day 0 and day 28

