**Group C:**

one vaccination with MV-ZIKA-RSP, high dose, on day 0 and placebo on day 28

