***Please note:***

*As this is a first in humans' study, the site should initially enroll a group of six participants and then pause with enrollment until these participants completed their Post Dose Safety Follow Up one week after the first vaccination. If no events as defined in section 8.9.1 "Safety Stopping Rule" are identified, the site should resume enrolling participants. If such events were identified, the investigators and the sponsor need to assess the risk of continuing the study and based on this assessment to decide if or if not, the study should be continued.*

The 48 participants will be distributed between the 4 groups using a randomisation ratio of 14 : 14 : 12 : 8 = A : B : C : D, with an adequate representation of high dose, low dose and placebo subjects (2 : 2 : 0 : 2 = A : B : C : D) within the first 6 subjects to allow for the safety evaluation after the first vaccination.

A subject will be considered enrolled once the first IMP administration has been performed according to randomisation.

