### 12.2 Methods of Statistical Immunogenicity Analysis

The immunogenicity analysis will compare the anti-zika-rsp VNT antibody geometric mean titre (GMT) in the Per Protocol (PP) analysis population between the treatment groups. GMTs and GMT ratios will be estimated by applying an analysis of variance including the factor treatment group. This will be done using  $\log_{10}$  transformed data and taking the anti-log of the resulting point estimates for the least squares means, least squares means differences and the corresponding 2-sided 95% CIs.

P-values will also be provided to compare GMTs between the treatment groups adjusted for multiple comparisons according to Tukey-Kramer. Seroconversion rates will be compared between groups using Fisher's exact test.

Seroconversion will be defined as anti-zika-rsp VNT titres  $\geq 20$ .

ZIKA-RSP- and measles- ELISA titres will be analysed as described above.

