### 12.3 Methods of Statistical Safety Analysis

The analysis of safety will be performed in the Safety Population.

AEs and concomitant diseases will be coded using the MedDRA coding dictionary.

Solicited AEs (reactogenicity):

Solicited local and systemic AEs gathered by the participants' diaries will be summarised for the 7-day period, by AE grading (mild, moderate, severe) and by treatment group. The number and percentage of participants with AEs will be presented. Fisher exact tests will be provided for a comparison of AE rates between treatment groups in summary tables.

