## **12.4 Determination and Justification of Sample Size**

A formal sample size calculation was not conducted. The sample size of 48 participants has been determined based on prior experience in evaluating the safety and immunogenicity of vaccines and is typical for early phase clinical studies. Sample size for this study was determined on grounds of feasibility and common practice in similar trials.

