## 2.13 Columns in Tables

Every treatment group has its own column in the analysis and an additional total column will be added. For OV tables, where all subjects are shown, there is an additional column with subject not randomized.

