| 1.2.1.5   | 2.2.1.5         | Concomitant Medications by ATC Level 2 and 3 (Safety Population)                         |  |
| 1.2.1.6   | n/a             | Vital Signs at Baseline (Safety Population)  | 
 
• Systolic blood pressure [mmHg]
 
• Diastolic blood pressure [mmHg]
 
• Pulse rate [beats/min]
 
  |

Adapted from:

Page 23 of 33

STAT03\_A Statistical Analysis Plan

Version 6.0, Effective Date 16-Feb-2018

Confidential and intellectual property of Assign DMB. No part of this document or its contents may be duplicated, referenced, published or otherwise disclosed in any form or by any means without prior written consent of Assign DMB.

|  |                 |  |   |
|--|-----------------|--|---|
|  |                 |  | 
 
• Temperature [C]
 
 |
| 1.2.2.1-1.2.2.6  | 2.2.2.4-2.2.2.5 | For preliminary analysis repeat tables 1.2.1.1-1.2.1.6 and for final analysis tables 2.2.1.4-2.2.1.5 for mITT population (if not the same as Safety Population). |   |
| NOTE: Prior/Concomitant Medication tables will also be provided for final analysis but including all Prior/Concomitant Medications reported during the study |                 |  |   |
| Immunogenicity Analysis   |                 |  |   |
| Zika-RSP VNT Antibody   |                 |  |   |
| n/a  | 2.3.1.1         | GMT of Zika-RSP VNT Antibody by Visit (mITT Population)  |   |
| n/a  | 2.3.1.2         | GMT of Zika-RSP VNT Antibody based on interval-censored data by Visit (mITT Population)  |   |
| n/a  | 2.3.1.3         | ANOVA for GMT of Zika-RSP VNT Antibody between treatment groups by Visit (mITT Population)   |   |
| n/a  | 2.3.1.4         | Seroconversion rate for of Zika-RSP VNT Antibody by Visit (mITT Population)  |   |
| n/a  | 2.3.1.5         | Positivity of Zika-RSP VNT Antibody by time point  |   |
| Zika-RSP ELISA Antibody   |                 |  |   |
| n/a  | 2.3.1.6         | GMT of Zika-RSP-ELISA Antibodies by Visit (mITT Population)  |   |
| n/a  | 2.3.1.7         | GMT of Zika-RSP-ELISA Antibodies based on interval-censored data by Visit (mITT Population)  |   |
| n/a  | 2.3.1.8         | ANOVA for GMT of Zika-RSP-ELISA Antibodies between treatment groups by Visit (mITT Population)   |   |
| n/a  | 2.3.1.9         | Seroconversion rate of Zika-RSP-ELISA Antibodies by Visit (mITT Population)  |   |

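### Visit 2 titre analyses keep groups A and C apart although both have had one high dose and nothing else, and no adverse event table is split by injection

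*Combined protocol and SAP*

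**What the plan says.** **Regimens.** Protocol 6.3 gives group A "two vaccinations with MV-ZIKA-RSP, high dose on day 0 and day 28" and group C "one vaccination with MV-ZIKA-RSP, high dose, on day 0 and placebo on day 28". Allocation is made "using a randomisation ratio of 14 : 14 : 12 : 8 = A : B : C : D" (Protocol 8.2). Protocol 12.4 states: "A formal sample size calculation was not conducted".

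**Titres.** Protocol 12.2 and SAP 2.6 compare geometric mean titres by an analysis of variance whose only factor is treatment group, report "the corresponding 2-sided 95% CIs", and add Tukey-Kramer p-values. SAP 5.2 has Days 0, 28 and 56 all analysed. SAP 7.1 lists "ANOVA for GMT of Zika-RSP VNT Antibody between treatment groups by Visit (mITT Population", has matching tables for the Zika and measles ELISA, and repeats the set for the per-protocol population.

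**Columns.** SAP 2.13: "Every treatment group has its own column in the analysis and an additional total column will be added". The total column combines all four groups, placebo included, so it does not serve as a pooled vaccine or pooled high-dose result.

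**Adverse events.** SAP 6.2.2 counts events up to Day 56 for the preliminary analysis and all events for the final one. SAP 2.6 applies one overall Fisher-Freeman-Halton test per table. Protocol 12.3 summarises solicited events over the 7-day diary period "by AE grading (mild, moderate, severe) and by treatment group". Protocol 11.7 has a 7-day diary after each of the two injections, but neither document says how the two periods are combined, and no table in SAP 7.1 is divided by injection.

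**The concern.** Up to the second injection, groups A and C are a random division of people treated alike under blind. A four-level factor at Visit 2 therefore does three unhelpful things. It estimates the high-dose response twice, from 14 and from 12 people, and never from 26. It includes an A-versus-C comparison where no treatment difference can exist. And it makes the multiplicity adjustment cover six pairs where three would do.

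This bears on the dose objective in Protocol 5.2. No group receives a single low dose through Day 56, because B is injected again on day 28. Visit 2 is thus the only point at which one high dose can be set against one low dose.

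For adverse events the difficulty is separate. The cumulative tables do not show whether reactions follow the first or the second injection. In group C, reactions after vaccine and reactions after saline are added together.

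**Working it through.** **Identical exposure at Visit 2.** Protocol 8.5.3 describes the immunogenicity blood draw before the second injection. The Day 28 titres of A and C therefore both reflect one high dose.

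**Inputs from the documents.** A = 14, B = 14, C = 12, D = 8; 14 + 14 + 12 + 8 = 48, which agrees with the stated total. The plan gives no precision or power figure to reproduce.

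**Standard errors.** With common standard deviation s on the log10 scale, the standard error of a difference is s × √(1/n₁ + 1/n₂). The percentage reductions do not depend on s.

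| Contrast at Visit 2 | Four groups | A and C pooled | Reduction |
|---|---|---|---|
| High v low, from A v B | √(1/14+1/14) = 0.378 | √(1/26+1/14) = 0.331 | 12.3% |
| High v low, from C v B | √(1/12+1/14) = 0.393 | 0.331 | 15.7% |
| High v placebo, from A v D | √(1/14+1/8) = 0.443 | √(1/26+1/8) = 0.404 | 8.8% |
| High v placebo, from C v D | √(1/12+1/8) = 0.456 | 0.404 | 11.4% |

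For high versus low, pooling gives the precision of 2/(1/26+1/14) = 18.2 per arm instead of 14.

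**Critical values.** The Tukey-Kramer value (studentised range divided by √2, 5% level) is 2.670 for four groups on 44 degrees of freedom and 2.424 for three groups on 45. The unadjusted t values barely differ (2.015 and 2.014), so an unadjusted interval narrows by the same percentage as the standard error.

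**Illustrative power.** The documents give no standard deviation for this assay, so s = 0.3 to 0.6 log10 is an assumption. For a true two-fold high-to-low ratio at Day 28, A versus B compared with A+C versus B:

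| s (assumed) | Tukey-adjusted | Unadjusted |
|---|---|---|
| 0.3 | 0.500 → 0.725 | 0.738 → 0.842 |
| 0.4 | 0.262 → 0.446 | 0.495 → 0.603 |
| 0.5 | 0.153 → 0.283 | 0.344 → 0.428 |
| 0.6 | 0.101 → 0.193 | 0.255 → 0.316 |

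**Adverse events.** The summary tables in SAP 7.1 run to Day 56 or to study end, by group, with no division by injection. The information exists: SAP 7.2 listing 2.4.1 carries both vaccination dates, and listings 2.4.3 and 2.4.19 carry event start date and time.

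If first-injection events were tabulated, the SAP's overall test would gain modestly from pooling. At assumed rates of 70%, 50% and 30% for high, low and placebo, its power is 0.387 with four groups and 0.450 with three. Over the four sets of assumed rates examined, the gain was 6 to 8 percentage points.

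**The case against.** The plan reports by assigned regimen. That matches an objective concerned with one or two vaccinations up to Day 56, and in a trial sized on feasibility a loss of 9% to 16% in standard error is moderate. Both points stand. They support keeping the four-group tables, not omitting the pooled ones.

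Several stronger readings are tempting, and the documents do not support them.

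- **That half the high-dose data are wasted.** All 26 participants appear in the tables, and all four groups feed the residual variance. The loss is in the contrasts and in the multiplicity count.
- **That the confidence intervals would narrow by 20% (high v low) and 17% (high v placebo).** Those figures multiply the gain in standard error by the lower Tukey value. Protocol 12.2 and SAP 2.6 state Tukey-Kramer for the p-values only and mention no adjustment of the intervals. The established narrowing is that of the standard error.
- **That a Day 28 adverse event analysis wrongly separates A and C.** There is no such analysis. Over the cumulative windows the two groups are different regimens and should stay apart. The gap is the missing table by injection.
- **That first- and second-injection reactions cannot be separated.** The listings allow it; only the summary is missing.
- **That pooling is needed for a tighter bound when no event occurs.** With zero events in both groups to Day 56, a reader can add two planned columns and obtain the one-sided 95% upper bound for 26 people, 1 − 0.05^(1/26) = 10.9%. A by-injection table helps only where events occur.
- **That the one-shot versus two-shot question in Protocol 4.5 is compromised.** That question is A versus C at Day 56, which the four-group plan already tests.

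One small caveat to pooling remains. Protocol 8.2 places two A participants and no C participants among the first six enrolled, so the groups differ slightly in enrolment time.

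**Conclusion.** The point holds as a cheap improvement, not as an error that invalidates a planned result. At Visit 2 the plan leaves 12% to 16% of the standard error unrecovered for high versus low and 9% to 11% for high versus placebo, and it uses a Tukey value of 2.670 where 2.424 would serve. These figures assume full arms and a common variance; exclusions from the per-protocol population would change them somewhat. The power figures rest also on the assumed standard deviations.

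For adverse events the finding is about presentation: no summary table separates the two injections, and group C's column combines reactions after vaccine with reactions after saline. Pooling A and C is justified only for data before the second injection.

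**What to change.** Add the following as supplements and keep the four-group Day 56 and cumulative adverse event tables. Protocol 12.6 allows the SAP to add analyses.

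1. **SAP 2.6, 5.1 and 7.1.** Add a Visit 2 titre analysis with three groups: high (A+C, 26), low (B, 14) and placebo (D, 8). Apply Tukey-Kramer over three groups, for both the per-protocol and mITT populations.
2. **SAP 2.13, 6.2 and 7.1.** Add solicited and related adverse event tables by injection. Pool A and C for events with onset before the second injection. Use four groups after it, where A versus C compares a second high dose with saline. State the denominator (those who received that injection) and a rule for events with incomplete start dates.
3. **SAP 2.14.** Record the additions there, since it now states that no changes from the protocol are planned.

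**Timing.** SAP 2.4 unblinds sponsor and analysis staff after the Day 56 snapshot. If that safety analysis has already been unblinded, label the adverse event additions post hoc. SAP 2.1 defers immunogenicity to the final analysis, so the Visit 2 addition should be recorded before titres are seen by treatment.

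**Cost.** Extra table programming and a few more tables; no new data.

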## 7.2 List of Data Listings

| No. for prel. Analysis             | No. for FA | Legend   | Content   |
|------------------------------------|------------|--|---|
| Overall Subject Information |            |  |   |
| 1.1.1                              | 2.1.1      | Analysis Population Details                              | Subject number, Treatment, received IMP, Safety Population, mITT Population, PP Population, Reason not in PP Population, Randomization performed, Reason randomization not performed, randomization date/time, randomization number   |
| 1.1.2                              | 2.1.2      | Screening Failures with Reason                           | Subject number, Date of informed consent, Reason for screening failure (Subject's withdrawal of consent, In/Ex criterion not fulfilled / exclusion criterion fulfilled, Other), Specification other reason  |
| 1.1.3                              | 2.1.3      | Violated Entry Criteria                                  | Subject number, Visit, Criterion ID not met, Criterion description  |
| 1.1.4                              | 2.1.4      | Attended Visits with Dates (Safety Population)           | Subject number, Treatment, Visit, date, age, Reason for visit not performed, reason for outside time window, reason for unscheduled visit   |
| 1.1.5                              | 2.1.5      | Protocol Deviations (Safety Population)                  | Subject number, Treatment, PD Category, Classification, Reason for classification, PD Description   |
| 1.1.6                              | 2.1.6      | Study Status (Safety Population)                         | Subject number, Treatment, Visit attendance status, Primary reason early termination/treatment discontinuation, Other reason specification, AE Term, Specify individual stopping rules, AE term (Stopping rules), Primary cause of death, Death date, Date of study discontinuation |
| Baseline Evaluation         |            |  |   |
| 1.2.1                              | n/a        | Demographic Information (Safety Population)              | Subject number, Treatment, Date of birth, Age [years], Gender, Childbearing potential, reason, specification other, Race, Specification other race  |
| 1.2.2                              | n/a        | Full Physical Examination at Visit 0 (Safety Population) | Subject number, Treatment, Examination performed, Reason not performed, Exam Date   |
| 1.2.3                              | n/a        | Medical History (Safety Population)                      | Subject number, Treatment, Condition, Preferred Term (MedDRA [Version]), SOC (MedDRA [Version]), Start date, End date, Ongoing at study end   |
| 1.2.4                              | 2.2.4      | Prior Medication (Safety Population)                     | Subject number, Treatment, Medication or therapy, ATC Level 2 (WHODD [Version]), ATC Level 3 (WHODD [Version]), Indication category, Indication, Dose, Dose Unit, Dose Unit other, Frequency, Frequency other, Route, Route other, Start Date, Ongoing at study end, End Date       |
| 1.2.5                              | 2.2.5      | Concomitant Medication (Safety Population)               | Subject number, Treatment, Medication or therapy, ATC Level 2 (WHODD [Version]), ATC Level 3 (WHODD [Version]), Indication category, Indication, Dose, Dose Unit, Dose Unit other, Frequency, Frequency other, Route,   |

Adapted from:

STAT03\_A Statistical Analysis Plan

Version 6.0, Effective Date 16-Feb-2018

Page 29 of 33

Confidential and intellectual property of Assign DMB. No part of this document or its contents may be duplicated, referenced, published or otherwise disclosed in any form or by any means without prior written consent of Assign DMB.

06092018

|                                |       |  |  |
|--------------------------------|-------|--|--|
|                                |       |  | Route other, Start Date, Ongoing at study end, End Date  |
| 1.2.6                          | n/a   | Vaccination History (Safety Population)                    | Subject number, Treatment, Visit, Any vaccination history within the last three years prior to screening, Any new vaccination history since screening, Date, Vaccination/Indication, ATC Level 2 (WHODD [Version]), ATC Level 3 (WHODD [Version]), |
| 1.2.7                          | n/a   | Concomitant Procedure (Safety Population)                  | Subject number, Treatment, Procedure, Start/End date, Ongoing at study end, Indication category, Indication  |
| 1.2.8                          | n/a   | Virology   | Subject number, Treatment, Virology test, Test performed, Reason, Result, Date   |
| Immunogenicity Analysis |       |  |  |
| n/a                            | 2.3.1 | Functional Antibodies Assessment (VNT) (mITT Population)   | Subject number, Treatment, Visit, Sample performed, Reason not performed, Sample ID, Date/Time of sample, Titer [IU/ml], Serconversion, positive/negative value  |
| n/a                            | 2.3.2 | Functional Antibodies Assessment (ELISA) m(ITT Population) | Subject number, Treatment, Visit, Sample performed, Reason not performed, Sample ID, Date/Time of sample, Titer [IU/ml], Serconversion, positive/negative value  |
| n/a                            | 2.3.3 | Measles Antibodies Assessment (mITT Population)            | Subject number, Treatment, Visit, Sample performed, Reason not performed, Sample ID, Date/Time of sample, Titer [IU/ml], positive/negative value   |
| n/a                            | 2.3.4 | T-cell details (mITT Population)                           | Subject number, Treatment, Visit, Sample performed, Reason not performed, Sample ID, Date/Time of sample, Titer [IU/ml], positive/negative value   |
| Safety Analysis         |       |  |  |
| Extent of Exposure      |       |  |  |
| 1.4.1                          | 2.4.1 | Extent of Exposure (Safety Population)                     | Subject number, Treatment, Date first vaccination, Date second vaccination, Treatment duration [days], Date informed consent, Date of last attended visit, Study duration [days]   |
| 1.4.2                          | 2.4.2 | Study Medication Details (Safety Population)               | Subject number, Treatment, Visit, Vaccination performed, Reason, Date/time   |
| Adverse Events          |       |  |  |
| 1.4.3                          | 2.4.3 | Adverse Events Part 1 (Safety Population)                  | Subject number, Treatment, AE Term, MedDRA PT, MedDRA SOC, AE type, Start date/time, End date/time, Medically attended, Severity, Serious AE, SAE Criteria, Relationship to Study Treatment  |
| 1.4.4                          | 2.4.4 | Adverse Events Part 2 (Safety Population)                  | Subject number, Treatment, AE Term, Action taken with Study Treatment, Other Action taken, specification other action taken, outcome, Ongoing at final examination   |
| 1.4.5                          | 2.4.5 | Unsolicited Adverse Events Part 1 (Safety Population)      | Subject number, Treatment, AE Term, MedDRA PT, MedDRA SOC, AE type, Start date/time, End date/time, Medically attended, Severity,  |

|        |        |  |  |
|--------|--------|--|--|
|        |        |  | Serious AE, SAE Criteria, Relationship to Study Treatment  |
| 1.4.6  | 2.4.6  | Unsolicited Adverse Events Part 2 (Safety Population)  | Subject number, Treatment, AE Term, Action taken with Study Treatment, Other Action taken, specification other action taken, outcome, Ongoing at final examination                 |
| 1.4.7  | 2.4.7  | Related Unsolicited Adverse Events Part 1 (Safety Population)  | See Listing x.4.5  |
| 1.4.8  | 2.4.8  | Related Unsolicited Adverse Events Part 2 (Safety Population)  | See Listing x.4.6  |
| 1.4.9  | 2.4.9  | Severe Unsolicited Adverse Events Part 1 (Safety Population)   | See Listing x.4.5  |
| 1.4.10 | 2.4.10 | Severe Unsolicited Adverse Events Part 2 (Safety Population)   | See Listing x.4.6  |
| 1.4.11 | 2.4.11 | Serious Unsolicited Adverse Events Part 1 (Safety Population)  | See Listing x.4.5  |
| 1.4.12 | 2.4.12 | Serious Unsolicited Adverse Events Part 2 (Safety Population)  | See Listing x.4.6  |
| 1.4.13 | 2.4.13 | Medically attended unsolicited Adverse Events Part 1 (Safety Population)                             | See Listing x.4.5  |
| 1.4.14 | 2.4.14 | Medically attended unsolicited Adverse Events Part 2 (Safety Population)                             | See Listing x.4.6  |
| 1.4.15 | 2.4.15 | Unsolicited Adverse Events caused Study Discontinuation Part 1 (Safety Population)                   | See Listing x.4.5  |
| 1.4.16 | 2.4.16 | Unsolicited Adverse Events caused Study Discontinuation Part 2 (Safety Population)                   | See Listing x.4.6  |
| 1.4.17 | 2.4.17 | Unsolicited Adverse Events leading to second Vaccination not administered Part 1 (Safety Population) | See Listing x.4.5  |
| 1.4.18 | 2.4.18 | Unsolicited Adverse Events leading to second Vaccination not administered Part 2 (Safety Population) | See Listing x.4.6  |
| 1.4.19 | 2.4.19 | Solicited Adverse Events Part 1 (Safety Population)  | Subject number, Treatment (Safety), Record ID, AE Term, Start date/time, End date/time, Medically attended, Severity, Serious AE, SAE Criteria, Causality                          |
| 1.4.20 | 2.4.20 | Solicited Adverse Events Part 2 (Safety Population)  | Subject number, Treatment (Safety), Record ID, AE Term, Action taken with Study Treatment, Other Action taken, Outcome, Ongoing at final examination, Caused study discontinuation |
| 1.4.21 | 2.4.21 | Related Solicited Adverse Events Part 1 (Safety Population)  | See Listing x.4.19   |
| 1.4.22 | 2.4.22 | Related Solicited Adverse Events Part 2 (Safety Population)  | See Listing x.4.20   |
| 1.4.23 | 2.4.23 | Severe Solicited Adverse Events Part 1 (Safety Population)   | See Listing x.4.19   |
| 1.4.24 | 2.4.24 | Severe Solicited Adverse Events Part 2 (Safety Population)   | See Listing x.4.20   |

|                                |        |  |  |
|--------------------------------|--------|--|--|
| 1.4.25                         | 2.4.25 | Serious Solicited Adverse Events Part 1 (Safety Population)  | See Listing x.4.19   |
| 1.4.26                         | 2.4.26 | Serious Solicited Adverse Events Part 2 (Safety Population)  | See Listing x.4.20   |
| 1.4.27                         | 2.4.27 | Medically attended Solicited Adverse Events Part 1 (Safety Population)                             | See Listing x.4.19   |
| 1.4.28                         | 2.4.28 | Medically attended Solicited Adverse Events Part 2 (Safety Population)                             | See Listing x.4.20   |
| 1.4.29                         | 2.4.29 | Solicited Adverse Events caused Study Discontinuation Part 1 (Safety Population)                   | See Listing x.4.19   |
| 1.4.30                         | 2.4.30 | Solicited Adverse Events caused Study Discontinuation Part 2 (Safety Population)                   | See Listing x.4.20   |
| 1.4.31                         | 2.4.31 | Solicited Adverse Events leading to second Vaccination not administered Part 1 (Safety Population) | See Listing x.4.19   |
| 1.4.32                         | 2.4.32 | Solicited Adverse Events leading to second Vaccination not administered Part 2 (Safety Population) | See Listing x.4.20   |
| Laboratory Parameters   |        |  |  |
| 1.4.33                         | n/a    | Hematology Values outside Normal Range (Safety Population)   | Subject number, Treatment, Visit, Date/Time, Parameter, Value, Unit, Not done, Reason not done, Clinically significant, Likely cause, Change from baseline                       |
| 1.4.34                         | n/a    | Clinical Chemistry Values outside Normal Range (Safety Population)                                 | Subject number, Treatment, Visit, Date/Time, Parameter, Value, Unit, Not done, Reason not done, Clinically significant, Likely cause, Change from baseline                       |
| 1.4.35                         | n/a    | Coagulation Values outside Normal Range (Safety Population)  | Subject number, Treatment, Visit, Date/Time, Parameter, Value, Unit, Not done, Reason not done, Clinically significant, Likely cause, Change from baseline                       |
| 1.4.36                         | n/a    | Abnormal and Positive Urinalysis Values (Safety Population)  | Subject number, Treatment, Visit, Date/Time, Parameter, Value, Unit, Not done, Reason not done, Clinically significant, Abnormal finding, Likely cause                           |
| Other Safety Parameters |        |  |  |
| 1.4.37                         | n/a    | Vital Signs (Safety Population)  | Subject number, Treatment, Visit, visit specifier, visit specifier, Vital signs collected, Reason not collected, Date/Time, Test, Result, Unit, Clinically significant, not done |
| 1.4.38                         | n/a    | Symptom-directed Physical Exam (Safety Population)   | Subject number, Treatment, Exam performed, Reason not performed, Exam date/Time  |
| 1.4.39                         | n/a    | System Based Physical Exam (Safety Population)   | Subject number, Treatment, Exam performed, Reason not performed, other reason, Exam date/time  |
| 1.4.40                         | n/a    | Local Tolerability (Safety Population)   | Subject number, Treatment, visit, visit specifier, Assessment performed, Reason not performed, Exam Date/Time  |

|        |     |                                    |   |
|--------|-----|------------------------------------|---|
| 1.4.41 | n/a | Pregnancy test (Safety Population) | Subject number, Treatment, visit, Pregnancy test performed, Reason not performed, Date/time, Result |
|--------|-----|------------------------------------|---|

